2.9.2 Deaths

Separate summaries for on-treatment deaths and all deaths will be produced by cohort, primary SOC, and preferred term. All deaths will be listed, and deaths in the post-treatment period will be flagged. A separate listing of deaths prior to start of treatment will be provided for all screened participants.

2.9.3 Laboratory data

For laboratory data assessments, data from all sources (central and local laboratories) will be combined. The summaries will include all laboratory assessments collected in the pre-treatment period (for baseline, if applicable) and on-treatment period. All laboratory assessments will be listed and those collected in the post-treatment period will be flagged in the listings.

For laboratory tests where NCI CTCAE grades are applicable, grading of laboratory values will be assigned programmatically as per NCI CTCAE version 5.0. The calculation of CTCAE grades will be based on the observed laboratory values (in SI units) only, clinical assessments will not be taken into account. CTCAE Grade 0 will be assigned for all non-missing values not graded as 1 or higher. Grade 5 will not be used. For laboratory tests where grades are not defined by CTCAE version 5.0, results will be categorized as low, normal, or high based on laboratory normal ranges.

The following summaries/listings will be generated separately for hematology, biochemistry, and cardiac enzymes laboratory data (by laboratory parameter and cohort):

For laboratory tests where grades are defined by CTCAE v5.0:

- Worst post-baseline CTC grade (regardless of the baseline status). Each participant will be counted only for the worst grade observed post-baseline
- Shift tables using CTC grades to compare baseline to the worst on-treatment value (hypo and hyper worst grade will be summarized separately, if applicable)

For laboratory tests where CTC grades are not defined:

- Shift tables using low, normal, high (as well as low and high combined) classification to compare baseline to the worst on-treatment value.

Listings of all laboratory data by participant and visit/time, with the corresponding CTCAE v5.0 grades, if applicable, and the classifications relative to the laboratory normal ranges will be provided. Lab data collected during the post-treatment period will be flagged. Urinalysis will be presented in listings and will not be summarized

Liver function parameters

Liver function parameters of interest are total bilirubin (BILI), ALT, AST and alkaline phosphatase (ALP). The number and percentage of participants with worst post-baseline values as per Novartis Liver Toxicity guideline will be summarized. Because the study protocol inclusion criteria allowed participants to be enrolled with elevated baseline (BL) ALT or AST values, these are distinguished in the assessment.

The following summaries will be produced:

- Peak post-baseline values
 - ALT > 3×ULN
 - ALT > 5×ULN
 - ALT > 10×ULN
 - ALT > 20×ULN

- AST > 3×ULN
- AST > 5×ULN
- AST > 10×ULN
- AST > 20×ULN
- ALT or AST > 3×ULN
- ALT or AST > 5×ULN
- ALT or AST > 8×ULN
- ALT or AST > 10×ULN
- ALT or AST > 20×ULN
- BILI > 2×ULN
- BILI > 3×ULN
- Combined elevations post-baseline
 - AST and ALT \leq ULN at baseline
 - (ALT or AST > 3×ULN) and BILI > 2×ULN
 - (ALT or AST > 3×ULN) and BILI > 2×ULN and ALP \geq 2×ULN
 - (ALT or AST > 3×ULN) and BILI > 2×ULN and ALP < 2×ULN
 - ALT or AST > ULN at baseline
 - (Elevated ALT or AST) and BILI > 2×BL and BILI > 2×ULN
 - (Elevated ALT or AST) and BILI > 2×BL and BILI > 2×ULN and ALP \geq 2×ULN
 - (Elevated ALT or AST) and BILI > 2×BL and BILI > 2×ULN and ALP < 2×ULN

Combined elevations post-baseline are based on the peak values at any post-baseline time for a participant.

(Elevated AST or ALT) is defined as:

- > 3×ULN if \leq ULN at baseline, or
- (> 3× baseline or > 8×ULN) if > ULN at baseline

Potential Hy's Law events are defined as those participants who, depending on their baseline status, fulfill one of the criteria, i.e., (ALT or AST > 3 x baseline) OR (ALT or AST > 8.0 x ULN), whichever is lower, combined with (BILI > 2 x baseline AND > 2.0 x ULN). Further medical review has to be conducted to assess potential confounding factors such as liver metastases, liver function at baseline etc.

In addition, a listing of the hepatic laboratory values (BILI, ALT, AST and ALP) will be provided with values x.x times above ULN and CTCAE grades flagged. Peak total bilirubin vs peak ALT/AST values will also be graphically presented (eDISH plot). If any participants are identified as potential Hy's law cases, a graph with the time course of liver chemistry values and dose will be prepared per participant.

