Fatigue/ Asthenia (General disorders and administ	ration site conditions)	
Grade 1 and 2	Recommendation: Maintain study treatment and dose level.	
Grade 3	Recommendation: Interrupt study treatment until resolved to ≤ grade 1, then:	
	If resolved in ≤ 7 days, maintain dose level.	
	If resolved in > 7 days, reduce 1 dose level.	
Ocular (uveitis, eye pain, blurred vision)		
Grade 1	Recommendation: Maintain study treatment and dose level. Ophthalmology consultation is required within 72 hours, except for dry eye.	
Grade 2	Recommendation: Interrupt study treatment.	
	Urgent ophthalmology consultation.	
	Upon resolution to ≤ Grade 1 in < 14 days, may consider reintroducing study treatment without dose reduction after discussion with the Novartis medical Monitor and consultation with ophthalmology.	
	Upon resolution to ≤ Grade 1 in ≥ 14 days, study treatment may be reintroduced at 1 lower dose level after discussion with the Novartis Medical Monitor and consultation with ophthalmology.	
Grade 3 and Grade 4	Mandatory: Permanently discontinue study treatment. Urgent ophthalmology consultation.	
Retinal vein occlusion or Retinal detachment		
Any Grade	Mandatory: Permanently discontinue study treatment. Urgent ophthalmology consultation.	
Other adverse events		
Grade 1 and 2	Recommendation: Maintain study treatment and dose level.	
Grade 3	Recommendation: Interrupt study treatment until resolved to ≤ grade 1, then reduce 1 dose level.	
	Mandatory: Interrupt study treatment for ≥ grade 3 vomiting or grade 3 nausea only if the vomiting or nausea cannot be controlled with optimal anti-emetic therapy (as per local practice).	
Grade 4	Mandatory: Permanently discontinue study treatment.	

^a Common Toxicity Criteria for Adverse Events (CTCAE Version 5.0)

^b Core LFTs consist of ALT, AST, GGT, total bilirubin (fractionated [direct and indirect], if total bilirubin > 2.0 x ULN), and alkaline phosphatase (fractionated [quantification of isoforms], if alkaline phosphatase > 2.0 x ULN)

 $^{^{\}rm c}$ "Combined" defined as total bilirubin increase to the defined threshold concurrently with ALT/AST increase to the defined threshold

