10.5 Appendix 5: Liver safety monitoring

To ensure participant safety and enhance reliability in determining the hepatotoxic potential of an investigational drug, a standardized process for identification, monitoring and evaluation of liver events has to be followed

Please refer to Table 10-1 in Section 10.5 for complete definitions of liver laboratory triggers.

Once a participant is exposed to study treatment, every liver event defined in Table 6-3 should be followed up by the Investigator or designated personnel at the trial site, as summarized below. Additional details on actions required in case of liver events are outlined in Table 10-1 and Table 10-2. Repeat liver chemistry tests (i.e. ALT, AST, TBL, PT/INR, ALP and G-GT) to confirm elevation.

- These liver chemistry repeats will be performed using the central laboratory. If results will not be available from the central laboratory, then the repeats can also be performed at a local laboratory to monitor the safety of the participant. If a liver event is subsequently reported, any local liver chemistry tests previously conducted that are associated with this event should have results recorded on the appropriate eCRF
- If the initial elevation is confirmed, close observation of the participant will be initiated, including consideration of treatment interruption if deemed appropriate
- Discontinuation of the investigational drug (refer to the Discontinuation of study treatment section), if appropriate
- Hospitalization of the participant if appropriate
- Causality assessment of the liver event
- Thorough follow-up of the liver event should include
 - These investigations can include based on Investigator's discretion: serology tests, imaging and pathology assessments, hepatologist's consultancy; obtaining more detailed history of symptoms and prior or concurrent diseases, history of concomitant drug use, exclusion of underlying liver disease

All follow-up information and procedures performed must be recorded as appropriate in the eCRF.

Table 10-1 Liver event and laboratory trigger definitions

Definition/ threshold
ALT or AST > 5 x ULN
 ALP > 2 x ULN (in the absence of known bone pathology)
 Total bilirubin > 3 x ULN (in the absence of known Gilbert syndrome)
ALT or AST > 3 x ULN and INR > 1.5
 Potential Hy's Law cases (defined as ALT or AST > 3 x ULN and Total bilirubin > 2 x ULN [mainly conjugated fraction] without notable increase in ALP to > 2 x ULN)

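### The SAP's potential Hy's Law sentence spells out only the raised-baseline criterion, so literal programming flags normal-baseline participants below 3 x ULN; it also leaves timing and ALP unstated

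*SAP*

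**What the plan says.** SAP section 2.9.3 (Liver function parameters) introduces the flag this way: "Potential Hy's Law events are defined as those participants who, depending on their baseline status, fulfill one of the criteria". What follows is a single criterion: "ALT or AST > 3 x baseline) OR (ALT or AST > 8.0 x ULN), whichever is lower, combined with" the bilirubin condition "BILI > 2 x baseline AND > 2.0 x ULN". No second criterion for normal baselines is given, and the sentence mentions neither timing nor ALP.

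Nearby text in the same section does separate the two groups. It notes that because participants could be "enrolled with elevated baseline (BL) ALT or AST values, these are distinguished in the assessment". The definition opening "Elevated AST or ALT) is defined as" sets >3 x ULN for an analyte at or below ULN at baseline, and keeps >3 x baseline or >8 x ULN for one above ULN. The combined-elevation rows use the same split, are subdivided by ALP, and carry their own timing rule: "Combined elevations post-baseline are based on the peak values at any post-baseline time for a participant".

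The protocol has three relevant places:

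- Table 6-3 and section 6.5.3.1: AST or ALT >3 x ULN with bilirubin >2 x ULN if AST, ALT and bilirubin were normal at baseline. The 3 x baseline or 8 x ULN limb applies if any of the three was raised.
- Table 6-3, footnote c: combined means "total bilirubin increase to the defined threshold concurrently with ALT/AST increase to the defined threshold".
- Table 10-1, which names potential Hy's Law cases: "defined as ALT or AST > 3 x ULN and Total bilirubin > 2 x ULN", with no notable ALP rise above 2 x ULN and no split by baseline.

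**The concern.** The wording promises a choice between criteria and supplies one. A programmer working from that sentence alone would apply a multiple of the participant's own baseline to people whose baseline was normal. For anyone below ULN at baseline, three times baseline is less than 3 x ULN, so the flag would fire on transaminase values that neither the protocol nor the adjacent SAP definition treats as meeting the threshold.

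The flag leads to medical review and a per-participant time-course graph. Hepatic effects are among the monitoring concerns in protocol section 2.3, and safety is a secondary objective. A flag whose meaning differs from the rows printed beside it, and from the protocol's use of the same term, is hard to interpret in the CSR. Silence on timing and ALP leaves two more choices to whoever programs it.

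**Working it through.** The SAP states no Hy's Law figure to reproduce, so the check compares thresholds. All are in multiples of ULN, for a baseline ALT or AST of b:

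- SAP Hy's Law sentence, read literally: min(3b, 8).
- SAP definition of elevated AST or ALT: 3 if b ≤ 1, otherwise min(3b, 8).
- Protocol Table 6-3 and 6.5.3.1: 3 if AST, ALT and bilirubin are all normal at baseline, otherwise min(3b, 8).
- Protocol Table 10-1: 3 for everyone.

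The documents give no baseline distribution, so the values of b are assumed. Their upper end is the eligibility limit of 3 x ULN (protocol 5.1). Baseline bilirubin is taken as normal in the table.

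| Baseline b | SAP sentence, literal | SAP elevated definition | Protocol 6-3 / 6.5.3.1 | Protocol Table 10-1 |
|---|---|---|---|---|
| 0.25 | 0.75 | 3.0 | 3.0 | 3.0 |
| 0.50 | 1.50 | 3.0 | 3.0 | 3.0 |
| 0.75 | 2.25 | 3.0 | 3.0 | 3.0 |
| 1.00 | 3.00 | 3.0 | 3.0 | 3.0 |
| 1.50 | 4.50 | 4.5 | 4.5 | 3.0 |
| 2.00 | 6.00 | 6.0 | 6.0 | 3.0 |
| 2.50 | 7.50 | 7.5 | 7.5 | 3.0 |
| 3.00 | 8.00 | 8.0 | 8.0 | 3.0 |

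The 8 x ULN arm takes over only when 3b > 8, that is, when b > 8/3 = 2.67. Below that, 3 x baseline governs, and it is under 3 x ULN whenever b < 1. When b < 1/3, 3b is below 1, so even a value inside the normal range would meet the transaminase part.

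The bilirubin part still has to be met. Its threshold is max(2 x baseline, 2 x ULN): 2.0 x ULN for any normal baseline, rising to 2 x 1.5 = 3.0 x ULN at the eligibility limit of 1.5 x ULN.

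Example, all normal at baseline: ALT baseline 0.5, peak ALT 1.6, bilirubin 2.1. The literal sentence is met (1.6 > 1.5 and 2.1 > 2.0). The SAP's normal-baseline combined rows and all three protocol definitions are not met (1.6 < 3).

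Two further results follow:

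- For raised baselines the sentence agrees with Table 6-3 and 6.5.3.1 but is stricter than Table 10-1 (7.5 against 3 at b = 2.5). It can therefore miss participants whom Table 10-1 would call potential Hy's Law.
- When only bilirubin is raised at baseline, protocol 6.5.3.1 itself uses min(3b, 8), giving 1.5 x ULN at b = 0.5. The SAP's elevated definition splits on the transaminase alone and gives 3.0.

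**The case against.** The best reply is that this is an unfinished sentence rather than a wrong rule. It says status depends on baseline, the section says raised baselines are handled separately, and the missing limb stands a few lines higher. A careful programmer might supply it. Flagged participants are only potential cases, the SAP requires medical review for confounders such as liver metastases, and the time-course graph would show whether the elevations coincided.

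Much of that stands, and it rules out several stronger readings that a reader might infer:

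- *That the SAP applies the raised-baseline rule to everyone.* The reference to baseline status contradicts this; the sentence is incomplete.
- *That the Hy's Law flag pairs non-concurrent peaks.* The peak rule is written for the combined-elevation rows, and the eDISH plot also uses peaks. The Hy's Law sentence states no timing at all.
- *That peaks or the absent ALP condition lower the transaminase threshold.* They do not; only the missing limb does.
- *That ALP is ignored.* The adjacent rows split by it and the hepatic listing includes it.
- *That the CSR will carry an inflated Hy's Law count.* No such table is specified. One participant is 1/90 = 1.1% of cohort A or 1/30 = 3.3% of cohort B, but those are arithmetic, not an estimate of how often this would occur.

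What the reply does not remove is the defect itself. The sentence states its own criterion instead of referring to the definition above it. Medical review comes after the flag, and it cannot recover participants whom the flag never picks up.

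**Conclusion.** The point holds as a defect of specification. The potential Hy's Law sentence omits the normal-baseline limb. Read literally, it sets a threshold of 0.75 to 2.25 x ULN for assumed baselines of 0.25 to 0.75 x ULN, against 3 x ULN in the protocol and in the SAP's own neighbouring definition. It also leaves timing and ALP unstated where the protocol addresses both. These thresholds rest on literal programming and on the assumed baselines; how many participants would be affected cannot be derived from the documents, and each would also need bilirubin above 2 x ULN.

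The protocol is not a single benchmark either: Table 10-1 has an ALP condition and no baseline split; Table 6-3 attaches its cholestasis exclusion to the normal-baseline limb; the triggers in 6.5.3.1 carry no ALP condition. The consequence is confined to a descriptive hepatic screen. No efficacy result depends on it.

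**What to change.** In SAP 2.9.3:

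1. Add the missing limb to the Hy's Law sentence: with normal baseline values, ALT or AST >3 x ULN with bilirubin >2 x ULN. Keep the existing limb for raised baselines only.
2. Say explicitly which limb applies when bilirubin alone is raised at baseline, since the SAP's elevated definition and protocol 6.5.3.1 differ there.
3. State that the flag uses concurrent elevations, and define concurrent operationally.
4. State how ALP is handled in each limb. An ALP exclusion should not be added to the raised-baseline limb by default, because Table 6-3 and 6.5.3.1 do not state one there.
5. Name the protocol definition that the flag implements. Table 10-1 must be reconciled with Table 6-3 and 6.5.3.1; which clinical definition prevails is for the sponsor's hepatic safety experts.

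The peak-at-any-time combined rows and the eDISH plot can stay as they are, labelled as a screen. In the SAP the cost is a few lines of text and one programmed flag, with no new data collection. The protocol reconciliation is a wording clarification.

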2.9.4 Other safety data

2.9.4.1 ECG and cardiac imaging data

12-lead ECGs including PR, QRS, QT and QTcF intervals and heart rate will be obtained for each participant during the study. ECG data will be read and interpreted centrally. The average of the ECG parameters at each assessment should be used in the analyses. ECGs collected during the on-treatment period will be summarized.

The number and percentage of participants with notable ECG values will be presented by treatment arm based on the categories below. ECG shift table based on notable values will also be presented by treatment arm.

- QT and QTcF
 - New value of > 450 and ≤ 480 ms
 - New value of > 480 and ≤ 500 ms
 - New value of > 500 ms
 - Increase from Baseline of > 30 ms to ≤ 60 ms
 - Increase from Baseline of > 60 ms
- HR
 - Increase from baseline $> 25\%$ and to a value > 100 bpm
 - Decrease from baseline $> 25\%$ and to a value < 50 bpm
- PR
 - Increase from baseline $> 25\%$ and to a value > 200 ms
 - New value of > 200 ms
- QRS
 - Increase from baseline $> 25\%$ and to a value > 120 ms
 - New values of QRS > 120 ms

A listing of all ECG assessments will be produced by cohort and notable abnormalities will be flagged. In the listing, the assessments collected during the post-treatment period will be flagged. In addition, descriptive statistical analysis (mean and standard deviation) by time point of assessment for Δ QTcF (QTcF change from baseline) will be carried out.

Left ventricular ejection fraction (LVEF) data will be reported on the “Cardiac Imaging” eCRF. The worst decrease in LVEF from baseline will be calculated for each participant (by subtracting the baseline LVEF % from the LVEF % at each post-baseline assessment) and summarized. The summary will include the number and percentage of participants regardless of the method used in the following notable LVEF values:

- Absolute decrease from baseline $\geq 10\% < 20\%$ or LVEF $\geq 40\% \leq 50\%$ (CTCAE grade 2)
- Absolute decrease from baseline $\geq 20\%$ or LVEF $\geq 20\% < 40\%$ (CTCAE grade 3)
- Absolute LVEF $< 20\%$ (CTCAE grade 4)

LVEF shift table to compare baseline to the worst post-baseline on-treatment value (the lowest value corresponds to “worst”) will also be presented.

Baseline categories is defined as follows:

- LVEF > 50%, LVEF \geq 40% \leq 50%, LVEF \geq 20% $<$ 40%, LVEF $<$ 20%

Post-baseline categories correspond to CTCAE grade, defined as follows:

- LVEF > 50%,
- Absolute decrease from baseline \geq 10% $<$ 20% or LVEF \geq 40% \leq 50% (CTCAE grade 2)
- Absolute decrease from baseline \geq 20% or LVEF \geq 20% $<$ 40% (CTCAE grade 3)
- LVEF $<$ 20% (CTCAE grade 4)

A listing of all cardiac imaging data will be produced by cohort and notable abnormalities will be flagged. In the listing, the assessments collected during the post-treatment period will be flagged.

2.9.4.2 Vital signs

Vital sign assessments are performed in order to characterize basic body function. The following parameters were collected: systolic and diastolic blood pressure (mmHg), pulse (beats per minute), body temperature (°C), respiratory rate (breaths per minute, brpm), weight (kg), and height (cm).

Vital signs collected during the on-treatment period will be summarized. The number and percentage of participants with notable vital signs values will be presented based on the categories below.

Clinically notable elevated values:

- Systolic BP: \geq 180 mmHg and an increase \geq 20 mmHg from baseline
- Diastolic BP: \geq 105 mmHg and an increase \geq 15 mmHg from baseline
- Body temperature: \geq 39.1°C
- Weight: an increase from baseline of \geq 10%
- Pulse rate: \geq 100 bpm with an increase from baseline of \geq 25%
- Respiratory rate: \geq 20 brpm with an increase from baseline of $>$ 20%

Clinically notable values below the normal values:

- Systolic BP: \leq 90 mmHg and a decrease \geq 20 mmHg from baseline
- Diastolic BP: \leq 50 mmHg and a decrease \geq 15 mmHg from baseline
- Weight: a decrease from baseline of \geq 10%
- Pulse rate: \leq 50 bpm with a decrease from baseline of \geq 25%
- Respiratory rate: \leq 8 brpm with a decrease from baseline of $>$ 20%

A listing of all vital sign assessments will be produced, and notable values will be flagged. In the listing, the assessments collected during the post-treatment period will be flagged.

2.9.4.3 ECOG performance status

The performance status will be assessed according to the ECOG performance status scale as specified in [Table 2-7](#) below, ranging from 0 (most active) to 5 (least active).

Table 2-8 ECOG performance status

Grade	ECOG status
0	Fully active, able to carry on all pre-disease performance without restriction
1	Restricted in physically strenuous activity but ambulatory and able to carry out work of a light or sedentary nature e.g., light house work, office work
2	Ambulatory and capable of all self-care but unable to carry out any work activities. Up and about more than 50% of waking hours
3	Capable of only limited self-care, confined to bed or chair more than 50% of waking hours
4	Completely disabled. Cannot carry on any self-care. Totally confined to bed or chair
5	Dead

The rules and time windows defined in [Section 2.1.3.9](#) will be used to group the ECOG PS data over time.

Frequency counts and percentages of participants in each score category will be provided by time point for the on-treatment period. Shift tables of ECOG performance status at baseline to worst post-baseline ECOG performance status by score will be provided by cohort using the safety set. ECOG performance status at each time point will be listed.

2.10 Analyses supporting secondary objectives – pharmacokinetic endpoints

To characterize the pharmacokinetics of JDQ443 is a secondary objective of the study. The PAS and FPAS will be used in pharmacokinetic data analysis and PK summary statistics. JDQ443 concentrations and PK parameters (as feasible) of non-Chinese, Chinese participants (subgroup 3) and all participants will be reported separately for each of the two cohorts.

PK concentrations

JDQ443 concentration data will be listed by cohort, participant, and visit/sampling time point using the PAS. Descriptive summary statistics will be provided by cohort and visit/sampling time point, including the frequency (n, %) of concentrations below the lower limit of quantification (anticipated LLOQ: 5 ng/mL).

Summary statistics will include n (number of participants with evaluable values), m (number of non-zero concentrations), mean (arithmetic and geometric), SD, coefficient of variation (CV; arithmetic and geometric), median, minimum, and maximum.

A graphical presentation will be provided on the mean concentration at each scheduled time point, when the full PK profile is available.

PK parameters

PK parameters such as listed in [Table 2-8](#) will be derived using non-compartmental analysis using Phoenix WinNonlin (Version 8.0 or higher) and reported, if feasible.

Descriptive summary statistics of PK parameters will include mean (arithmetic and geometric), SD, CV (arithmetic and geometric), median, minimum, and maximum. An exception to this is T_{max} where median, minimum, and maximum will be presented.

Table 2-9 Non-compartmental pharmacokinetic parameters

AUC _{lastss}	The AUC from time zero to the last measurable concentration sampling time (t _{lastss}) at steady-state (mass × time × volume ⁻¹)
AUC _{tau}	The AUC calculated to the end of a dosing interval (tau) at steady-state (amount × time × volume ⁻¹)
C _{maxss}	The maximum (peak) observed plasma, blood, serum, or other body fluid drug concentrations after single dose administration (mass × volume ⁻¹)
T _{max,ss}	The time to reach maximum (peak) plasma, blood, serum, or other body fluid drug concentration at steady-state (time)
C _{min,ss}	Observed concentration at the end of a dosing interval (taken directly before next administration) at steady-state
Lambda _z	Smallest (slowest) disposition (hybrid) rate constant (time ⁻¹) may also be used for terminal elimination rate constant at steady-state (time ⁻¹)
T _{1/2,ss}	The elimination half-life associated with the terminal slope (λ_z) of a semi logarithmic concentration-time curve at steady-state (time).
CL/F	The total body clearance of drug from the plasma (volume × time ⁻¹)
V _{z/F}	The apparent volume of distribution during terminal phase (associated with λ_z) (volume)

Handling of PK data below LLOQ

All concentration values below the LLOQ are set to zero by the Bioanalyst and will be displayed in the listings as zero and flagged. LLOQ values will be treated as zero in any calculations of summary statistics and treated as missing for the calculation of the geometric means and their CV%. The number of non-zero concentrations will also be reported in the summary statistics.

Missing data for any PK data will not be imputed and will be treated as missing.

